### **Intervention for 9 months:**

#### **Vitamin D:**

Participants will receive a 30-day supply of 2000 IU vitamin D to take by mouth once a day at about the same time every day. If baseline Vitamin D is low, we will supplement with Cholecalciferol for two weeks as follows:

Participants with Serum Vitamin D:

< 10 ng/mL, will receive 5,000 IU daily

11-20 ng/mL, will receive 2000 IU daily

21-40 ng/mL, will receive 1000 IU daily

Then, all participants will receive 2000 IU daily through the period of intervention.

Vitamin D will be refilled every 25 days to ensure the participants do not run out of the intervention drug.

We will also call participants every 30 days for a pill count to ensure that they are taking the vitamin D.

#### **Resistance training (RT) and Rowing Exercise:**

Those assigned to the NMES-RT/Rowing with Vitamin D group will receive 4.5 months of electrical leg shocks with ankle weights (no ankle weights in the first week), twice a week. The intervention will be done while sitting in a wheelchair. Two adhesive patches (electrodes) will be placed on the skin over the knee muscles. Participants/caregivers will initiate and slowly increase electric current on the stimulator in 5-second intervals to cause full leg extension (leg straightens out). Once full knee extension is achieved in a sitting position, an extra 2 lbs. of weight will be added every week. Each session will consist of 4 sets of 10 knee extensions and will last for 30-40 minutes. Training will alternate between the right and left leg. In addition, the participant and a caregiver will train on how to set up the device for use at home.

After 4.5 months, each participant will receive a rowing machine (Murtisol Magnetic Rowing machine) to use twice weekly. The participant will be asked to transfer to the rowing machine (with assistance or supervision from a caregiver) for the intervention, using a sliding board or a portable lift. Participant/caregiver will place patches for NMES on both knee extensors (muscles that straighten out the legs) and flexors (muscles that

bend the knee) and initiate the electrical current. They will alternate the current 5 seconds on, then 10 seconds off on both muscle groups. Participants with upper body strength will be encouraged to use their arms to initiate the extension and flexion of both legs. If they do not have full trunk control, they will be provided with an adhesive belt to secure their trunk during an exercise and a special hand mitten to secure their hands to the rowing machine, if needed. Each session will consist of 4 sets of 10 knee extensions and flexions, and it will last for 30 - 40 minutes. Training will alternate between the right and left legs on the same day.

#### **Passive range of motion or passive stretching:**

Participants assigned to the passive exercise and Vitamin D group will have their caregivers perform passive ROM. Caregivers will be instructed to sit on a stool, cup the participant's leg above the ankle joint, and move it from 90-degrees of knee flexion to full knee extension. The leg will be maintained in extension for 5 sec and returned to flexion for 5 sec. The passive actions are repeated in the manner described in the RT protocol; 10 reps on the right leg followed by 10 reps on the left leg for 4 sets x 10 reps. This exercise training will take place twice a week. Each training exercise will last 30 – 40 minutes each day of the exercise.

**Blood Pressure (BP) Monitoring:** The caregiver will measure the participant's BP before starting the exercise, record the reading and leave the BP cuff in place. About 15 to 20 minutes into the exercise, another BP reading will be taken and the final reading at the end of the exercise to safeguard against Autonomic Dysreflexia (AD). Most individuals with high cervical and thoracic levels of SCI own BP machines. However, if they do not own one, they are eligible to get one from their Providers.

#### **Caregiver Role**

Caregivers will train on the use of neuromuscular electrical stimulation and passive range of motion (ROM). After the training, the caregivers will be responsible for placing and removing skin electrodes (patches) and checking the skin afterward for skin breakdown. The caregivers will also be responsible for adjusting the stimulator current. For those undergoing passive ROM, the caregivers will be responsible for moving the paralyzed legs (one at a time) while holding them above the ankle, from 90 degrees of knee flexion (bent knee) to full knee extension (straighten out). They will also be responsible for adding ankle weights during the exercise every week. Additionally, the caregivers will assist with transfers (if participants were unable to do so). We will review transfer techniques with a sliding board or portable lift with caregivers if the participant or caregiver requests us to do so. Caregivers and persons with SCI are usually skilled in the use of these types of transfer equipment.

#### **Home Video Telehealth Service:**

Telehealth is a service offered by the VA for use to provide virtual care. Telehealth uses video conference calls. Suppose participants are not already enrolled in the VA Telehealth program. In that case, they will be given a registration form to complete to provide us permission to use VA Telehealth before they can participate. The participants will need to have a smartphone, a tablet, or a computer with a webcam and

internet access to be able to participate. However, if they not have one of these, they will be provided a tablet with a web camera and internet access, and we will help them create an e-mail account if they do not already have one.

The participants will need a quiet space in their homes for the training. The study team will make sure that the address is accessible to EMS in an emergency. If it is not accessible to EMS, they may not participate in the study. At the start of each session, the PI will verify the address and telephone number and an alternate contact person, and a phone number for use in emergencies or communication failure. Should the need arise, the study team will contact EMS or the National VA Telehealth Crisis Line for additional help.

Before starting the exercise training session, the microphone, speakers, and web camera will be tested to ensure things are working fine from both ends. We will request participants to be ready 20-30 min before the video call by asking the caregivers to place the electrodes on their legs, make sure the batteries of the stimulator are fully charged, electrodes are connected to the stimulator, and the ankle weights are positioned. Once the setup is completed, and the Telehealth connection is established, the training will begin.

All training sessions will be conducted twice weekly. At the end of each session, the PI will confirm the next appointment and request that the participant confirms his/her next appointment online 24 hours before the next session. If unable to keep the next appointment for any reason, we can reschedule the appointment for another day and time so long as participants can have two sessions in a week.

#### **WHO-Quality of Life (QOL) Survey:**

Participants will be given a survey regarding their health, wellness and QOL to determine whether exercise programs could enhance QOL after SCI. The WHO-QOL is a survey that rates six broad domains on health (physical, psychology, level of independence, social relations, environment, and spirituality/religion/personal belief), using a five-point scale (1-5) to produce a total of 100 items in the assessment. Participants will be given the survey at the beginning and at the end of the study. The survey takes about 15 minutes to complete.

**Measurements:** All training aspects and measurements will be conducted at the Central Virginia VA Health Care System (CVHCS) SCI Exercise Physiology & Body Composition Laboratory. All participants will undergo bone assessment measurements with MRI and DXA (**specific aim 1**); measurements of bone biomarkers and weekly dietary recalls (**specific aim 2**). All testing procedures will be conducted a week to training (**baseline**) and post-intervention for **Aim 1** and **baseline, 4.5 mos and 9 mos** for **Aim 2**. Will get MRI of thigh skeletal muscles to determine muscle CSA, trabecular bone parameters (including BMF), cortical porosity and CSA. To ensure consistency of dietary intake for protein, sodium, calcium, and phosphorous, team dietitian will contact participants once a month to advise on diet. Evaluation of participants will involve

cardiovascular assessments (EKG), heart and carotid auscultations, assessment of jugular venous pulse, peripheral pulses to identify any significant factors that may impact cardiovascular health, respiratory assessment (inspection, palpation, percussion, lungs auscultation, pulse oximetry and respiratory rate), and assessment of pain. Blood analysis will include: BALP, P1NP, CTX, 25-(OH)D, PTH, complete renal panel, calcium, magnesium and Hemoglobin A1c. While previous work from our institution used urinary NTX, the current standard for bone resorption test is considered to be serum CTX. These markers will be obtained fasting at baseline, 4.5 months and 9 months; and would require no more than 10ml of blood sample (each time) from study participants.

**Vit D: Each participant will be prescribed a 30-day supply of oral 2000 IU of Cholecalciferol (Vit D3), daily.** The Endocrine Society guidelines recommend treating Vit D deficiency with Vit D3 to achieve a target 25(OH)D goal of 30 ng/mL. Vit D deficiency is defined as 25(OH)D <20 ng/mL and insufficient as 25(OH)D 21 ng/mL to 29 ng/mL. Participants with insufficient 25(OH)D3 will receive Vit D3 supplementation for 2wks as follows: Vit D < 10: 5000 units daily for 2 weeks; Vit D 11-20: 2000 units daily for 2 weeks; Vit D 21-40: 1000 units daily for 2 weeks. All participants will then receive 2000 units of Vit D for the rest of the study period. We chose to use 2000 IU of daily Vit D3 supplementation because prior studies have reported physiologic levels of 25(OH)D with this dose. Participants will be instructed to take their Vit D3 at about the same time every day. The prescription will be renewed every 25 days to allow for early mailing to participants. To monitor compliance, study participants will be called every 30 days for pill counts. Pre-treatment levels of 25(OH)D, will be measured at commencement of treatment and post treatment at 4.5 months and 9 months; participants with Vit D insufficiency will receive higher doses of Vit D3 supplement for 2 weeks prior to intervention. The values obtained will be entered in a spread sheet.

**Resistance training (RT):** Participants and caregivers will be trained on RT (application of electrodes, initiating and adjusting currents and the application of ankle weights). Resistant Training will be performed twice weekly **in an open-chain format (resistance is placed at the distal part of an extremity in a fixed position) in the first 4.5 mos, followed by 4.5 mos in a closed-chain format using surface NMES.** Initial open-chain format ensures muscle hypertrophy that is likely to cause modest bone adaptations, prior to it being subjected to significant loading during closed-chain format. This would ensure bone safety during the close kinematic exercise. No ankle weights in the first week to ensure full knee extension against gravity. Weekly increments of 2 lbs. will be used on the condition that full knee extension is achieved before any increase in load. NMES of the extensor muscles of the knee, for concentric-eccentric actions will be by surface electrodes as shown in **fig 1**. Two 8 X10 cm^2 (Uni-Patch, Wabasha, MI, USA) adhesive carbon electrodes will be placed on the skin over the knee extensor muscle group. Current from the stimulator will be increased at 5-second intervals to evoke full knee extension against gravity followed by the lengthening action during relaxation. The current (mA) that causes full knee extension will be recorded. Training will be performed remotely, twice weekly for 4 sets of 10 repetitions under full supervision from the PI **by telehealth**. Each RT session will consist of 4 sets of 10 repetitions of NMES-induced knee extensions for 60 min. A 5 sec/5 sec work/rest ratio will be used with 3 min rests between sets, 30 Hz, 1 ms pulses and current

sufficient to evoke full knee extension. To perform a closed kinematic chain exercise, participants will use a commercially available rowing machine (Murtisol Magnetic Rowing machine) to perform 4 sets x 10 reps twice weekly. NMES rowing has been shown to provide compressive loading on both distal femur and proximal tibia, further enhancing trabecular bone health in persons with chronic SCI. Participants will transfer to the rowing machine with assistance by the caregiver or significant other, using a sliding board or a portable lift if available at home. Most Veterans have a portable lift in their homes as part of their clinical care. Additionally, persons with paraplegia are trained to manage fall risks and get back to their manual wheelchair with minimal assistance from caregiver. This will provide them with an opportunity to transfer to and from their manual wheelchairs and rowing machine. Surface NMES will be applied to stimulate knee extensors for extension, alternating with the hamstrings for flexion, assisted by the upper extremities, with progression under full supervision by the trained caregiver. Electrodes will be placed bilaterally on both knee extensors and flexors and the current will be alternated 5 sec on/10 sec off on both muscle groups with frequency set at 30 Hz, pulse duration at 1 ms and reasonable amplitude to cause flexion/extension. This approach was previously adopted for our lab.

**Passive range of motion (ROM) or passive stretching for the control group:**

**Participants and caregiver will be trained on passive ROM.** A trained caregiver sits on a stool and cups participant's leg proximal to the ankle joint and move it from 90-degrees of knee flexion to full knee extension. The leg will be maintained in extension for 5 sec and returned to flexion for 5 sec. The passive actions is repeated in the manner described in the RT protocol; 10 reps on the right leg followed by 10 reps on left leg for a total of 4 sets x 10 reps. This will help to balance the design between the two groups and training will be conducted twice weekly.

**Home Video Telehealth Service:** Home exercise training will be conducted using Video Telehealth services, (known as, VA Video Connect (VVC)), under guidance from the Office of Connected Care with management and oversight from the VISN Telehealth Manager and Facility Telehealth Coordinator. The telehealth Program is located in the SCI&D service. The applicant is versed in the use of Telehealth for patient care as this has been the primary mode of patient evaluation and treatment during this COVID-19 pandemic. After obtaining participant's consent, the PI, together with the Telehealth Coordinator, will conduct a selection-consideration review for all participants, to ensure they agree to VVC for training, review clinical "video into home" worksheet and availability of appropriate technology. Participants without appropriate technology will be issued a tablet with web camera and internet access and assisted to create an e-mail account if they do not already have one. All participants who agree to provide a private, conducive environment for in-home training at addresses accessible to EMS, in emergency situations, will be enrolled. At the start of a session, the PI will obtain the address and telephone numbers of participants for use in emergency situations during VVC. Should the need arise, the PI can contact the local medical/telehealth emergency resources for back-up or contact the National Study Participant's Crisis Line for additional help. Before starting the exercise training session, the microphone, speakers and web camera are tested for efficacy in the home for both study participant and PI. The PI will ensure the availability of a telephone backup in the event of a communication failure via VVC. Participants will be advised to be ready 20-30 min prior

to the VVC by placing electrodes, ensuring the batteries of the stimulator are charged overnight, connecting the electrodes to the stimulator and positioning the ankle weights. Once the setup is completed and internet connection established, the participant is instructed to increase the current to bring the leg into full knee extension and then report the current in milliamps (mA) to the PI. The goal is for each participant to perform 4 sets of ten repetitions. Each exercise training session will be conducted for at least 30 min with 2-3 min of rest periods between each set and 5 sec between each repetition. At the end of each session, the PI confirms the next appointment, reminds participant to confirm next appointment online 24 hours before, and access their log in password. Our telehealth platform is well established with strong support from our IT department. It is unlikely to fail but should it fail, participant will be rescheduled for the next day.

**Measurements: Specific aim 1. MRI:** MRI with no contrast will be performed using a 3 Tesla magnet (GE). The skeletal muscle CSAs will be determined at baseline and 9 months, respectively. Both lower limbs will be strapped together using soft Thera-band to avoid any movement inside the magnet. Participants will be instructed to lie still inside the magnet and they will be provided with earplugs to protect their ears against the magnet noise. Duration of the whole scan including preparation time should not exceed 10 min. Images of both thighs will be obtained with the following scanning parameters (repetition time, 500; echo time, 14; field of view, 20cm; matrix, 256×256). Transaxial images, 8 mm thick and 4 mm apart, will be taken from the hip joint to the knee joint using a localized coil. A specific knee coil will be used to capture trabecular bone parameters of the distal femur and proximal tibia. Images will be downloaded and analyzed using X-vessel software for muscle/cortical bone CSAs, as previously conducted by our group.

**Trabecular Bone Assessment:** A 3D fast gradient-echo sequence will be used to obtain the high-resolution images (10 cm FOV), with a spatial reconstructed resolution of 195·195·1000 lm. A bilateral phased array coil (USA Instruments) will be used to obtain 30 contiguous 1mm slices in the axial plane, starting with the distal end of the femur, and another block of 30 starting with the proximal end of the tibia. A 3-D low-pass filter will be applied to correct for heterogeneous signal across the phased array surface coil. Regions of interests will be manually identified, and a set of parallel lines rotated by 5 through the slice to determine mean intercept length. Parameters measured will be apparent trabecular bone volume to total volume (app.BV/TV) and apparent trabecular thickness (app.Tb.Th, mm), from which apparent trabecular number (app.Tb.N, mm) and separation (app.Tb.Sp, mm) will be derived.

**Assessment of Trabecular Microarchitecture:** Within manually drawn regions of interest with the distal femur and proximal tibia trabecular bone, we will apply digital topological analysis and volumetric topological analysis to compute metrics of bone microarchitecture including trabecular thickness, trabecular separation, trabecular plate width, and network area density (1/mm) as in prior work, as well as BMF. In digital topological analysis, local connectivity and topological metrics are used to characterize different topological structures in a skeletal surface representation of a three-dimensional trabecular bone network. Volumetric topological analysis extends digital topological analysis and, through fuzzy skeletonization and unique manifold distance analysis approaches, will allow assessment of trabeculae on a continuum of plates to rods, permitting computation of individual trabecular plate width.

**Dual energy x-ray absorptiometry (iDXA):** iDXA will be used to measure bone composition including regional and total *Fat Mass (FM)*, *Fat Free Mass (FFM)*, cortical porosity, and BMD. Total body and regional scans will be performed using an iDXA scanner (Lunar Inc., Madison, WI) bone densitometer to determine regional BMD and total body T-score, Total hip BMD and knee BMD scores (Total body T-score less than -2.5. Total hip BMD T-scores < -3.5 and knee BMD scores of less than 0.6 g/cm^2, will be excluded). Testing is performed after lower extremity elevation for at least 20 min to minimize fluid shift. Scanning and analysis is certified by DXA operator. The participant is assisted to lie on a padded table with both legs strapped proximal to the knees and ankles. The arms and legs are properly aligned to allow participant to lie still for 10 min during the scan. Total and regional FM and FFM are determined with DXA software in order to control for confounding variables; fat mass and BMF may influence bone health. The coefficient of variability of two repeated scans is < 3%.

**Specific aim 2:** We will assess bone remodeling with the following bone biomarkers: *BALP*, *P1NP* and *CTX*, 25(OH)D, PTH, renal panel, magnesium and calcium levels at baseline, 4.5 mos and 9 mos. HgbA1c will be obtained prior to and post intervention to determine glucose uptake benefit resulting from the intervention. Blood samples not exceeding 10 mls will be obtained after 8-10 hours overnight fasting. Samples will be processed at CVHCS Clinical Pathology Laboratory or Quest diagnostic depending on negotiated cost. All tests will be performed at the VAMC and participants transportation to and from test will be sponsored.

#### Pilot exploratory work for Both Groups

[figure not shown]
We will investigate the effects both groups on Toll-like receptors (TLRs), and Natural killer (NK) on T cell functionality (CD4+ T cells), cytokines, interferons, or chemokines, including IL-6, IL-10, IFN- $\alpha$ , IFN- $\gamma$  and IP-10 in persons with chronic SCI. Peripheral Blood Mononuclear Cells (PBMCs) will be collected from all participants at three time points and isolated by Ficoll gradient centrifugation for immune analyses. For immune alteration of myeloid cells, the phagocytic and bactericidal function of circulating neutrophils in response to *Staphylococcus aureus* will be analyzed as described previously. Impairment in recognition of pathogen-associated molecular patterns by toll-like receptors (TLRs) and subsequently declining immune responses have been associated with immune dysfunction, PBMCs will be incubated with various ligands for TLRs, followed by assessment of production of cytokines, interferons, or chemokines, including IL-6, IL-10, IFN- $\alpha$ , IFN- $\gamma$  and IP-10. To assess T cell functionality, PBMCs will be cultured in the presence of phorbol 12-myristate 13-acetate plus ionomycin and subjected to assays of IFN production by intracellular staining and flow cytometry. Natural killer (NK) cells represent the main components of lymphocyte-mediated innate immunity and play an indispensable role in combating bacterial and viral infections. These cells have been reported to be associated with SCI-induced immune deficiency. Expression of CD107a, the marker of NK cell cytotoxicity, as well as production of effector cytokines TNF- $\alpha$  and IFN- $\gamma$  by NK cells will be examined. NK cell cytotoxicity will also be assayed using the target cell line K562 on the basis of lactate dehydrogenase release assay as described. Additionally, plasma collected from patients will be analyzed for immune-related cytokines including IL-10, which has been

identified to be a common candidate for immune suppression induced by stress and injury, including injury in the central nervous system. Samples will be analyzed at the VCU Immunology Department.

**Pitfalls and Alternatives:** Changes in trabecular bone parameters may be indeterminate because of the smallness and heterogeneity of sample size. We will rely on previous experience to calculate the effect size, and on that basis, adequately power future trials. **Failure to recruit proposed sample size:** The applicant's primary mentor ([name]) successfully conducted similar clinical trials in the past and demonstrated that use of telehealth facilitated recruitment and compliance among Veterans with SCI. Additionally, we may recruit non-Veterans to ensure completion of the study within the proposed timeline. [name] has a dual appointment with VCU and can successfully collaborate with VCU to ensure recruitment of the target sample size.

**Statistical Analyses.** After signing consent, the PI will randomly assign a number from 1-20 to participants using a computer program (nQuery). The order of enrollment will determine the participant's number based on level and duration of injury. Summary of information, including means and SD, frequencies and percentages, for all study variables will be calculated at all-time points. T-tests and Pearson chi-square tests will be used to compare characteristics that may act as confounders, including age, level and time since injury.

**Sample Size Justification:** Being a pilot study, consideration of sample size is just to allow determination and examination of preliminary evidence of efficacy and effect size estimation towards a larger future randomized trial. The proposed sample size of 10 per group is adjudged sufficient to accomplish these goals. Although Julious recommends a sample size of at least 12 per group on the basis that gain in precision for estimates of variance becomes relatively small on reaching a sample size of 12, we are unable to meet that target because of cost of the intervention and testing. Our sample size still allows for adequate accuracy. As shown in **Fig 6**, the gain in precision is still limited with a sample size of 10 per group. Although testing efficacy is not the primary goal, we will have 80% power to detect a standardized mean difference of  $d=0.9$  using an alpha of 0.25 corresponding to a large effect size. Type I error rates larger than 0.05 are often used and recommended for pilot studies where tests of efficacy are not the primary aim.

**Data Analysis Plan:** IBM SPSS statistical software version 26 will be used. Being a pilot study, primary analyses will be mainly descriptive. Means and SD will be estimated for utilization (number of sessions completed), with each outcome. Finally, analysis of covariance (ANCOVA) will be used to test differences between groups post intervention for each outcome, using the baseline score as a covariate. If normality of groups appears to be violated in the sample normalizing transformations or non-parametric statistics will be considered.

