
effect size. Our results support the fact that the TRT+RT has a small effect size (<0.3) on parameters of trabecular bone at the distal femur and moderate effect size at proximal tibia (>0.5-0.8) compared to TRT only. Biostatistician advised that we should not run inferential statistics (**Holman et al. under review, Ost. Int.-R2**)

**Summary of preliminary data.** There are two key questions that are yet to be answered before deployment of this intervention; **1) Would NMES+RT +Vit D drive improvement in trabecular bone parameters compared to passive movement + Vit D in persons with chronic SCI? and 2) does skeletal muscle hypertrophy induce improvement in biomarkers of bone formation over bone resorption?** Our preliminary data is limited; however, it highlights the benefits of evoking skeletal muscle hypertrophy on trabecular bone parameters in persons with chronic SCI. We therefore posit that a home-based approach of 9 mos NMES-evoked RT and Vit D supplementation will enhance trabecular bone parameters and markers of bone formation compared to passive movement and Vit D supplementation.

Fig. 4

**Research Design and Methods:** A 2-year single site randomized controlled trial to investigate the efficacy of NMES-RT + Vit D versus passive movement + Vit D supplementation on trabecular bone parameters of distal femur and proximal tibia and on biomarkers of bone formation and resorption in persons with chronic SCI. All Recruitment will be conducted at CVHCS

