**Benefits:**

**Potential benefits of research to Veterans and others:**

The proposed study is geared towards improving both bone and muscle strengths and will benefit the participants in increasing muscle blood flow, blood glucose uptake as well as decrease bone demineralization. The anticipated benefits of the current trial should be viewed in the light that the proposed work will serve as a pilot work for future protocols by providing supporting preliminary data to adequately power future clinical trials.

We hope findings from this work will provide supporting evidence to establish the resources necessary to **accelerate research and development of therapies for bone loss**

**attenuation and improved functionality and quality of life for persons with chronic SCI.** It is anticipated that this will reduce the costs associated with managing low impact fractures secondary to bone loss after SCI. The PI will make every effort to disseminate the knowledge gained from this trial through presentations at local, national and/or international scientific meetings. And also, by manuscript preparations and submission to high impact peer-reviewed journals for publications. The intervention in this study may directly benefit participants physiologically, aside from the financial compensation, by increasing muscle mass and improving blood flow. However, if there are no direct benefits to participants, the information gained, has the potential to help others in the future.

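### Ten per group is too few for the pilot's effect size alone to size a later trial, and the stated accuracy rests on a rule about variance

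*Combined protocol and SAP*

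**What the plan says.** Under Sample Size Justification, the size of the trial is tied to "determination and examination of preliminary evidence of efficacy and effect size estimation towards a larger future randomized trial", and "The proposed sample size of 10 per group is adjudged sufficient to accomplish these goals". The paragraph cites a published recommendation of at least 12 per group, on the ground that the "gain in precision for estimates of variance becomes relatively small on reaching a sample size of 12". It says cost prevents meeting that number, and then states: "Our sample size still allows for adequate accuracy". It points to Fig 6, which is not reproduced in the text. It also gives 80% power for d = 0.9 at an alpha of 0.25, while saying that testing efficacy is not the main goal.

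Under Pitfalls and Alternatives, after conceding that the bone results may be inconclusive in a small and mixed sample, the plan says it will draw on previous experience to "calculate the effect size, and on that basis, adequately power future trials". The section on potential benefits describes the trial as "providing supporting preliminary data to adequately power future clinical trials".

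The Data Analysis Plan calls the primary analyses mainly descriptive and adds an ANCOVA of each outcome on its baseline value.

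The previous experience is in Preliminary Study. There the trabecular effect sizes are described as differences between baseline and post-intervention in nine participants of the testosterone-plus-training arm. The closing summary reads "Our results support the fact that the TRT+RT has a small effect size (<0.3" and goes on to set these effects against testosterone alone.

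**The concern.** An effect size meant to inform a later trial needs an interval narrow enough to separate trials of very different size. The text gives no interval width and no precision target for the effect size, so nothing in it shows that 10 per group is enough for this purpose. The cited rule concerns a different quantity, the variance, and the plan does not meet its number.

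The sentence on previous experience does not say whether the effect size will come from this pilot or from the earlier study. Either source is a poor basis. The pilot's d is imprecise. The earlier d has no control group, covers 16 weeks instead of 9 months, and includes testosterone, which this trial does not give.

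At stake is the size of the follow-on trial. If it is sized on a chance-high estimate, it is likely to miss a real benefit. If it is sized on a chance-low one, it wastes participants or is never started.

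**Working it through.** **Inputs.** 10 per group, d = 0.9, alpha 0.25 and power 80% (Sample Size Justification); ANCOVA on baseline (Data Analysis Plan); no attrition expected (Detailed Strategies for the Recruitment Plan); before-after means and standard errors (Preliminary Study). The sidedness of alpha and the baseline-to-follow-up correlation are not given.

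**1. The plan's own figure.** Noncentrality = 0.9 × √(10/2) = 2.01. With a two-sided alpha of 0.25 and 18 df the critical t is 1.19, and the power is 79.6% (80.6% by the normal approximation). The stated 80% reproduces if alpha is two-sided; one-sided it would be about 91%.

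**2. Interval for d at 10 per arm, unadjusted.** Invert the noncentral t with t = d × √5 and 18 df, then divide the limits by √5. For d = 0.5, t = 1.118, the noncentrality limits are -0.890 and 3.096, and so the limits for d are -0.40 and 1.38.

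| Observed d | 95% CI | Width | Width at 12 per arm |
|---|---|---|---|
| 0 | -0.88 to 0.88 | 1.75 | 1.60 |
| 0.5 | -0.40 to 1.38 | 1.78 | 1.63 |
| 0.9 | -0.04 to 1.81 | 1.85 | 1.69 |

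Meeting the 12-per-group benchmark would therefore change little. A half-width of about 0.5 SD needs about 30 per arm.

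**3. What that means for a next trial.** For 80% power at two-sided 0.05, n per arm = 2(1.96 + 0.84)²/d² = 15.70/d², rounded up. An observed d of 0.5 gives 15.70/0.25, or 63 per arm. Its upper limit of 1.38 gives 15.70/1.904, or 9 per arm. Its lower limit is compatible with no benefit.

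**4. Sizing on the observed d.** I used 400,000 simulated pilots (normal outcomes, 10 per arm), each followed by a trial sized with the formula in step 3. The last two columns assume that the next trial is run only after a favourable result at two-sided 0.25.

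| True d | n per arm needed | Too small, all pilots | Too small, if observed d > 0 | Too small, if favourable at 0.25 | Mean true power, if favourable at 0.25 |
|---|---|---|---|---|---|
| 0.3 | 175 | 50% | 67% | 100% | 20% |
| 0.5 | 63 | 50% | 58% | 100% | 41% |
| 0.7 | 33 | 51% | 54% | 78% | 58% |
| 0.9 | 20 | 50% | 51% | 63% | 68% |

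The 100% entries follow directly from the filter. A favourable result at 0.25 requires d above 1.189 × √(2/10) = 0.532, so the next trial can never exceed 15.70/0.283, or 56 per arm, against 63 needed at a true d of 0.5.

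**5. The preliminary d values.** For proximal tibia plate width, 30.56/22.52 = 1.357, and 1.357/√8 = 0.48, as reported. For proximal tibia spacing, -0.25/0.17 = -1.471, and -1.471/√8 = -0.52, as reported. For distal femur plate width, 11.7/42.70 = 0.274, and 0.274/√8 = 0.10, as reported. The reported interval half-widths of about 0.69 match 1.96/√8. The first two would be 0.45 and -0.49 with √9, so the divisor does not match the stated nine participants exactly. All the same, the values are scaled from within-arm changes, as Preliminary Study itself describes them.

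**6. Precision of the mean difference.** The unadjusted half-width is 2.101 × √(2/10) = 0.94 SD. With ANCOVA (17 df) it is approximately 2.110 × √(2/10) × √(1 - r²), ignoring any chance baseline imbalance. The correlation r is an assumption: r = 0.5 gives 0.82 SD, r = 0.7 gives 0.67 and r = 0.9 gives 0.41. With losses and no adjustment, 9 per arm gives 1.00 SD and 8 per arm gives 1.07.

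**7. Upper limit for the SD.** The one-sided 80% limit is SD × √(df/χ²), with χ² at its 20th percentile. This is 1.18 × the pooled SD at 18 df, or 1.19 × the ANCOVA residual SD at 17 df.

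**The case against.** The strongest reply is that the plan is modest about itself. It is a pilot with mainly descriptive analyses, it concedes that results may be inconclusive, and it admits missing the 12-per-group benchmark. All of that is true.

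A reader might call the accuracy statement false. The documents do not support that: the plan sets no numerical target that could be breached, and Fig 6 cannot be seen. If the statement is meant for the variance, it is not unreasonable. The 95% limits for the SD are 0.76 to 1.48 times the estimate at 10 per group and 0.77 to 1.42 at 12. What stands is that the text does not support the statement for the effect size, which is the purpose named in the same paragraph.

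A reader might also infer that the plan commits itself to putting the pilot's own d into a sample-size formula. The sentence refers to previous experience and could describe a fallback for an inconclusive pilot. The wording on effect-size estimation and on preliminary data links the pilot to later trials only loosely. This ambiguity does not make the sentence safe, because the other source is a before-after effect.

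The planned ANCOVA may narrow the interval, perhaps substantially. The documents give no correlation, so the gain can only be shown as a range.

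Finally, this trial's own sample size is not derived from the preliminary d values, so their wording is a background inconsistency unless they are used for later planning.

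**Conclusion.** The concern holds in a limited form. At 10 per arm the unadjusted 95% interval for d is about ±0.9 SD, so the point estimate cannot by itself size a later trial, and the claim of adequate accuracy is unsupported for that purpose. The sentence on powering future trials is unsafe whichever source it means.

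It would go too far to say that the next trial will be too small. Sized on the observed d alone, it is too small in about half of pilots. The error runs mainly in that direction only if a favourable pilot is a condition for proceeding. No passage makes the 0.25 level a condition for proceeding, so the figures of 20% and 41% true power at d = 0.3 and 0.5 rest on that assumption.

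All figures assume normal outcomes, equal groups and no attrition. The conduct and validity of this trial's own comparison are not affected; the point concerns what its result can be used for.

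**What to change.** 1. In Pitfalls and Alternatives, replace the sentence on previous experience. State that the next trial will be sized on a minimum worthwhile difference set in advance and on an upper confidence limit for the SD. Add that neither the pilot's observed d nor the preliminary before-after d will be used for this.
2. In the Data Analysis Plan, report for each outcome the ANCOVA-adjusted mean difference with its 95% interval, and the SD with a one-sided 80% upper limit. Use 1.18 × the pooled SD (18 df) if the next trial will be analysed unadjusted, or 1.19 × the residual SD (17 df) if by ANCOVA. Recompute both multipliers if participants are lost.
3. In Sample Size Justification, replace the accuracy statement with the expected 95% half-width for the mean difference: about 0.94 SD unadjusted, and 0.82, 0.67 or 0.41 SD with ANCOVA if the baseline correlation is 0.5, 0.7 or 0.9, labelled as assumptions.
4. In Preliminary Study, reconcile the closing comparison with testosterone alone with the description of the values as within-arm changes.

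The cost is wording and a few extra reported figures, with no added participants or visits. The downside is that the stated precision will read less favourably.
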